4.2 General trial design

There will be a 2-stage consent procedure for the trial, including a first consent for basic disease, age information, and HLA-typing (or the use of already available information in the patients' file; such information even if based on testing before the screening period is acceptable) since a large proportion of the patients (approximately half of the patients) will not match the HLA-A2 prerequisite to receive the HLA-A2 specific EO2040 immunization compound. The reason for the initial minimized consent (related to the procedure of HLA-testing, and before testing also establishing based on available information that the patient is eligible in relation to CRC type, prior therapy, and has an age ≥ 18 years) is to spare the necessity of all other testing for possible enrollment in the trial for patients who are not known to be HLA-A2 positive.

The second stage of the consent procedure will be related to treatment, and follow-up aspects of the trial procedures.

[REDACTED]

Study treatments will be administered until study treatment termination criteria as outlined in [Section 5.3.3](#) are fulfilled, e.g. reaching maximum study treatment period (6 months), unacceptable toxicity, or relapsing disease. At the time of stopping study treatment, appropriate other treatment will be advised by the treating physician on an individual patient basis. The patient should continue, even if study treatment is stopped, study follow-up measures for as long as the individual patient consent for follow-up is not withdrawn, the site is open, and the study not terminated per plan, or early, but for a maximum length of 3 years after start of study treatment.

All assessments of possible relapse in the trial will be determined at the sites by the principal investigators, or designees, according to the standard clinical criteria used at the site.

Of note, there is no current knowledge publicly available regarding the potential of pseudoprogression at immunotherapy in patients with ctDNA defined MRD of CRC. Thus, at scanning, especially at the 3-month study timepoint, if a relapse is indicated by scanning it is recommended to, if at all possible, also document the relapse with histology or cytology.

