8.1.2 Serious Adverse events

A serious adverse event (SAE) is any untoward medical occurrence that at any dose fulfills one or more of the following criteria:

- results in death,
- is immediately life-threatening,
 - *the term “life-threatening” in the definition of “serious” refers to an event in which the patient was at immediate risk of death at the time of the event; it does not refer to an event which hypothetically might have caused death if it were more severe,*
- results in persistent or significant disability/incapacity,
 - *disability is defined as a substantial disruption in a person’s ability to conduct normal life functions (i.e. the AE resulted in a significant, persistent, or permanent change, impairment, damage, or disruption in the patient’s bodily function/structure, physical activities, or quality of life),*
- is a congenital anomaly/birth defect,
- requires inpatient hospitalization or prolongation of existing hospitalization, and
 - *a hospitalization is defined as an inpatient overnight stay, but this can be shorter than 24 hours,*
- is another medically significant event defined as an event that may not be immediately life-threatening or result in death or hospitalization but may jeopardize the patient or may require intervention to prevent any of the above listed outcomes.

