8.1.2.1 Excluded events

Hospitalization for the following reasons will not be regarded as serious (i.e. will not be immediately reportable):

- routine treatment or monitoring of the disease under study, including hospitalization due to trial-related procedures, not associated with any deterioration of the patient’s status,

- elective or pre-planned treatment (before signing the ICF) for a pre-existing condition that is unrelated to the disease under study and has not worsened since signing the ICF,
- treatment on an emergency outpatient basis for an event not fulfilling any of the definitions for an SAE and not resulting in hospital admission,
- underlying disease progression (the CRC which is the basis for the patient enrollment in the trial) and events which are unequivocally (without doubt) related to the disease progression, and
- social reasons, respite care, and in the absence of a medical condition.

In addition, as also outlined in [Section 8.5.1](#), progression of the underlying disease or an AE unequivocally (without doubt) related to the progression of the underlying disease, regardless of its outcome or seriousness criteria, does not need to be reported as a SAE. However, the medical conditions and underlying diseases associated with disease progression needs to be captured on the AE eCRF page (as a non-serious AE). An SAE must be reported only if there are clinical symptoms/signs that cannot be without doubt associated with the progression of the underlying disease.

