8.5 Reporting by the investigational site

8.5.1 Adverse events

Any AE (including SAEs), whether, or not considered to be causally related to the trial medication and regardless of its seriousness, must be described and recorded in the AE section of the patient's eCRF on an ongoing basis.

A pre-existing condition is a clinical condition (including a condition being treated) that is diagnosed before the patient signs the ICF and that is documented as part of the patient's medical history; any clinically significant worsening of a pre-existing condition constitutes an AE. Also, any recurrence of a pre-existing condition is an AE.

The questions concerning whether the condition existed before the start of the active phase of the study and whether it has increased in severity and/or frequency will be used to determine whether an event is a TEAE. An AE is considered to be treatment-emergent if it is not present when the active phase of the study begins and is not a chronic condition that is part of the patient's medical history, or it is present at the start of the active phase of the study or as part of the patient's medical history, but the severity or frequency increases during the active phase. The active phase of the study begins at the time of the first dose of the study drug. The active phase of the study ends at the post-treatment visit for safety assessment (see **Table 8**).

A standardized question such as "Have you had any health problems since your last visit or since you were last questioned?" will be given by the Investigator or the investigational site personnel at each contact with the patient.

Progression of the underlying disease or an AE unequivocally (without doubt) related to the progression of the underlying disease, regardless of its outcome or seriousness criteria, does not need to be reported as an AE/SAE. However, the medical conditions and underlying diseases associated with disease progression needs to be captured on the AE eCRF page (as a non-serious AE). An SAE must be reported only if there are clinical symptoms/signs that cannot be without doubt associated with the progression of the underlying disease.

Whenever possible, a diagnosis rather than symptoms should be provided (e.g. anemia instead of low Hb).

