8.5.2 Documenting in the eCRF

The reported term should be a medical diagnosis or sign/symptom of the event, not a procedure. Each symptom in a constellation of symptoms should be listed separately if the Investigator has not made a preliminary/tentative summary diagnosis.

Fluctuations or re-occurrences of a condition, which are considered normal for the patient and are recorded in patient’s eCRF medical history, do not need to be reported as an AE. However, if the condition deteriorates during the trial it needs to be captured as an AE.

If the same AE occurs repeatedly, it must be assessed and documented separately each time if there are "AE-free" time periods between the AEs.

If possible, each AE should be evaluated to determine:

- event term or a description of the AE in medical terms (not as reported by the patient),
- severity grade as assessed by the Investigator (1 - 5 per NCI CTCAE v5.0),
- its causal relationship to study treatment(s) as assessed by the Investigator (suspected; not suspected),
- event duration, including onset date and end date,
- action taken with study treatments due to the reported event (dose not changed; drug interrupted, drug withdrawn; other),

- other action taken (no action taken; medication required; surgical intervention required; other),
- event seriousness (non-serious or serious AE),
- event outcome (recovered/resolved, recovered/resolved with sequelae, not recovered/not resolved, fatal, unknown), and
- disease progression-related event (yes, no).

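### Protocol 8.1.2, 8.1.2.1 and 8.5.1 conflict on progression-attributed events, so a fatal or hospitalizing event can be stored as a non-serious AE

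*Protocol*

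**What the plan says.** Protocol 8.1.2 defines a serious event by its consequences. Death is one criterion, and another is that the event "requires inpatient hospitalization or prolongation of existing hospitalization". Section 8.1.4 adds that seriousness follows from outcome or action criteria and guides regulatory reporting.

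Section 8.1.2.1 then lists exclusions, with progression of the underlying CRC among them: "Hospitalization for the following reasons will not be regarded as serious (i.e. will not be immediately reportable". Its closing paragraph goes beyond hospitalization. Progression, or an AE unequivocally related to it, "regardless of its outcome or seriousness criteria, does not need to be reported as a SAE", yet the associated condition "needs to be captured on the AE eCRF page (as a non-serious AE").

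Section 8.5.1 repeats that paragraph with one change. Here such an event, "regardless of its outcome or seriousness criteria, does not need to be reported as an AE/SAE". The requirement for a non-serious entry on the AE page follows directly. Both sections close with the same limit: "An SAE must be reported only if there are clinical symptoms/signs that cannot be without doubt associated with the progression of the underlying disease".

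Section 8.5.2 asks, for each AE, for outcome (fatal is one option), seriousness, causality and a flag, "disease progression-related event (yes, no").

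**The concern.** Three things are run together: whether the event is an AE, whether it is serious, and whether it must reach pharmacovigilance within 24 hours. Sparing sites expedited reports of plain relapse is a reasonable aim, but the text achieves it by changing the seriousness value itself.

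Two consequences follow. SAEs are a named component of the first secondary endpoint (Protocol 3.2.2), and their incidence would leave out events that meet 8.1.2. In addition, the exemption rests on the investigator's certainty, and neither section requires that relapse be confirmed. Section 4.2 leaves relapse to site criteria, only recommends histology or cytology, and says that "there is no current knowledge publicly available regarding the potential of pseudoprogression" with immunotherapy in this setting. Section 1.1.4 names the liver as the most common metastatic site, and Table 6 lists hepatitis among the immune-related reactions to nivolumab. A liver event could therefore be attributed to the wrong cause.

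**Working it through.** There is no planned figure to reproduce, so the check sets the rules side by side.

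| Place (Protocol) | Is it an AE? | Is it serious? | SAE report? |
|---|---|---|---|
| 8.1.2 and 8.1.4 | Any untoward occurrence | Yes, if fatal or hospitalizing | Follows from seriousness |
| 8.3.1 | All AEs, whatever the cause | SAEs unrelated to treatment included | Yes, to 30 days after the last dose; no progression exception |
| 8.1.2.1, hospitalization list | Not addressed | No, glossed as not immediately reportable | No |
| 8.1.2.1, closing paragraph | Yes, AE page | Entered as non-serious | No, unless in doubt |
| 8.5.1, pre-existing conditions | Yes, any recurrence | Not addressed | Not addressed |
| 8.5.1, progression, first sentence | Need not be reported as one | Criteria set aside | No |
| 8.5.1, progression, second and third sentences | Yes, AE page | Entered as non-serious | No, unless in doubt |

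**Step 1: AE status.** The first progression sentence in 8.5.1 conflicts with its own second sentence, with 8.1.2.1 and with 8.3.1. It also conflicts with the earlier rule in 8.5.1 on pre-existing conditions. Those are conditions diagnosed before consent and documented in the medical history. Resected CRC fits that description, so its recurrence is an AE under one paragraph and need not be reported as one under another.

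**Step 2: seriousness.** Take a patient who is hospitalized with, and dies of, a complication that the investigator attributes to relapse without doubt. Under 8.1.2 the event is serious on two criteria. Under 8.1.2.1 and 8.5.1 it is entered as non-serious. Under 8.5.2 its outcome is fatal and its progression flag is yes. A site that follows every instruction produces a fatal, non-serious record.

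**Step 3: effect on the endpoint.** In patients:

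SAE count under 8.1.2.1 and 8.5.1 = SAE count under 8.1.2 − patients whose only serious events were attributed without doubt to progression.

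The documents give no value for the last term. They do not state how often relapse in this population leads to hospitalization or death during the reporting period.

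**Step 4: wrong attribution.** If the investigator has doubt, an SAE report is due and the route works. If the investigator is certain but wrong, the event is entered as non-serious and the 24-hour notification in 8.5.3 does not start. The gap is therefore confined to confident misattribution.

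**Step 5: carry-through.** SAP 7.1.2 lists CRF data as documented, so the coded seriousness passes unchanged into the output. SAP 3.1 and 7.1.1 plan listings and no tables, for one treated patient.

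**The case against.** Section 8.1.2.1 is a subsection of 8.1.2 and can be read as a stated exception. A count under a narrower, prespecified definition is not an incorrect count. On this view the only real defect is the extra AE waiver in 8.5.1, and a site that reads the whole paragraph would still make the AE-page entry.

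Much of this stands, and it rules out several stronger readings that a reader might infer:

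- **That progression events are not AEs at all.** The sentence after the waiver requires an AE-page entry.
- **That SAE counts are wrong.** They would be counts under a narrower rule, and the SAP tabulates none.
- **That deaths and SAEs cannot be reconciled.** Section 8.5.1 provides a death page with date and causes, 3.2.2 lists deaths separately from SAEs, and the 8.5.2 fields can be cross-checked. A death may still have no matching SAE.
- **That a misread immune reaction escapes safety reporting.** Doubt triggers an SAE report, 8.4.1 requires a causality judgement that considers timing and known reactions, and 6.4.1 requires work-up of suspected immune-related reactions.
- **That the number of affected patients can be estimated.** Any such figure needs a rate of serious events after relapse, which the documents do not supply. It would also count true progression events, not misattributed reactions.

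The pseudoprogression remark in 4.2 concerns relapse suggested by a scan, so it gives only general support. Parts of 4.3, 8.5.3 and 8.6 are redacted, and whether such events receive further review cannot be judged.

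The objection does not remove two faults. The sections still disagree on AE status. The exception also goes beyond waiving a report: it prescribes a seriousness value that contradicts the recorded outcome and the definition in 8.1.2.

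**Conclusion.** The conflict is real and needs reconciling. As written, a compliant site can store a fatal or hospitalizing event as non-serious, and SAE incidence leaves out serious events attributed to progression. A serious reaction confidently but wrongly attributed to progression would miss the 24-hour route. The existing safeguards make this a narrow gap.

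The size cannot be stated in patients. For the design of 17 patients per cohort, it depends on an event rate that the documents do not give. For the study as it is ending, it is limited to the listings of one treated patient. This is a wording fault that should be corrected because correction is cheap. The documents do not show that the safety data are unreliable. The conclusion rests on the visible text and would need another look if redacted passages already separate seriousness from expedited reporting.

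**What to change.** Use one rule, worded identically in 8.1.2.1 and 8.5.1:

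1. Enter the event on the AE page with its true seriousness under 8.1.2 and its true outcome, and set the existing progression flag in 8.5.2. Delete the AE waiver from 8.5.1, and say how the rule on recurrence of pre-existing conditions applies to the CRC itself.
2. Limit the exemption to 24-hour expedited reporting, and keep the clause that any doubt about attribution requires an SAE report. Refer to the exemption in 8.3.1 and 8.5.3, which at present make no visible exception for progression.
3. Reconcile the exemption with 5.3.3, which refers to relapse confirmed on a scan. The reporting sections rely on the investigator's certainty alone.
4. List SAEs with and without flagged events, showing seriousness, outcome and flag side by side.

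The cost is a wording change in two sections with cross-references in two more, and a slightly higher SAE count. The flag already exists, no treatment or visit changes, and sites still send no expedited report for clear progression.

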8.5.1.1 Adverse Events Associated with an Overdose or Error in Treatment Administration

Study drug overdose is the accidental, or intentional, use of the drug in an amount higher than the dose being studied. An overdose, or incorrect administration, of study drug is not an AE unless it results in untoward medical effects.

Any study drug overdose or incorrect administration of study drug should be noted on the Study Drug Administration eCRF page.

All AEs associated with an overdose or incorrect administration of study drug should be recorded on the AE eCRF page. If the associated AE fulfils serious criteria, the event should be reported to the Sponsor immediately (i.e., no more than 24 hours after learning of the event; see [Section 8.5.3](#) for reporting instructions).

8.5.2 Documenting in the eCRF

The reported term should be a medical diagnosis or sign/symptom of the event, not a procedure. Each symptom in a constellation of symptoms should be listed separately if the Investigator has not made a preliminary/tentative summary diagnosis.

Fluctuations or re-occurrences of a condition, which are considered normal for the patient and are recorded in patient’s eCRF medical history, do not need to be reported as an AE. However, if the condition deteriorates during the trial it needs to be captured as an AE.

If the same AE occurs repeatedly, it must be assessed and documented separately each time if there are "AE-free" time periods between the AEs.

If possible, each AE should be evaluated to determine:

- event term or a description of the AE in medical terms (not as reported by the patient),
- severity grade as assessed by the Investigator (1 - 5 per NCI CTCAE v5.0),
- its causal relationship to study treatment(s) as assessed by the Investigator (suspected; not suspected),
- event duration, including onset date and end date,
- action taken with study treatments due to the reported event (dose not changed; drug interrupted, drug withdrawn; other),

- other action taken (no action taken; medication required; surgical intervention required; other),
- event seriousness (non-serious or serious AE),
- event outcome (recovered/resolved, recovered/resolved with sequelae, not recovered/not resolved, fatal, unknown), and
- disease progression-related event (yes, no).

8.5.3 Immediately reportable events - Serious Adverse Events & Pregnancies

The Investigator or designated investigational site staff must immediately (within 24 hours of awareness at the latest) notify/report to pharmacovigilance at the Sponsor, [REDACTED], any initial or medically relevant follow-up information about SAEs, or pregnancies (see [Section 8.2](#)).

All immediate reports from the investigational site to the Safety Group (i.e. SAEs and pregnancy reports) must also be recorded in the site's source documentation.

The primary mode of reporting a SAE is based on entering the appropriate and complete information into the clinical database via the SAE reporting form and submitting the SAE form [REDACTED] the trial Safety Group within 24 hours of obtaining knowledge of the event.

The SAE Form [REDACTED] is to collect data surrounding the event (e.g. the nature of the symptom[s], time of onset in relation to initiation of therapy, duration, intensity, and whether, or not therapy was interrupted or discontinued). The Investigator's assessment of the probable cause of the event will also be included. In addition, relevant medical history, concomitant medications, laboratory and diagnostic test reports, and procedures as well as all pertinent medical information related to the event will also be collected. [REDACTED] the site will submit it to the safety group within the system. Then an alert from the clinical database will be initiated and sent to the Safety Group. The Safety Group will generate the SAE report, a PDF extracted from the clinical database, and send to the Sponsor.

The Safety Group will generate SAE queries requesting missing information, correction of implausible, etc., and add the queries directly in the clinical database. It is the Investigator's responsibility to be diligent in providing the answer as soon as it is available by entry of the corrections in the eCRF and submission of the follow-up SAE report to the Safety Group.

[REDACTED]

Note, SAE report forms must be completed in English.

When a paper form is completed, follow-up information should not be reported on the same form that was used for the initial reporting, but using a new form filled in only with the new information. Changes/completions need to be done in a Good Clinical Practice (GCP)-compliant manner (i.e. dated and initialized). Originals of the report forms must be kept in the site study file (if certified electronic signature is available at site, electronic copy of the form is acceptable).

Initial reports of SAEs should never be left on telephone voicemails. In case of using the paper SAE form, please always fax or e-mail the SAE report, and follow-up with a telephone call if needed.

Serious AEs to be reported to the Enterome/ [REDACTED]

[REDACTED] [REDACTED]
[REDACTED] [REDACTED]

In case of urgent questions regarding SAE reporting please call:

[REDACTED] [REDACTED]
[REDACTED] [REDACTED]

The initial Pregnancy Data Collection form should be handled in the same way as an initial SAE report, i.e. via the EDC system, or via the specific paper form (latter only in case of technical issues with the EDC).

Follow-up information is to be sent within the same timelines using the same modes of reporting as outlined above.

All sites will follow their institutional requirements for submission of SAEs to their IRBs/IECs.

The processing and reporting of all relevant SAEs to authorities will be done by the Sponsor or Sponsor’s designee according to all applicable rules/regulations, including reporting of unexpected serious adverse events to the USA FDA according to 21 CFR 312.32. The Sponsor or designee will inform all investigational sites about reported relevant events according to applicable regulations.

[REDACTED]
[REDACTED]
[REDACTED]

[REDACTED]
[REDACTED]

[REDACTED]
[REDACTED]
[REDACTED]
[REDACTED]
[REDACTED]
[REDACTED]

